6.4. Multicenter Studies

This study will be conducted by multiple investigators at multiple sites. As the summaries of these data are descriptive in nature, no adjustments for site differences will be made.

6.5. Multiple Comparisons/Multiplicity

No multiplicity control measures will be used.

6.6. Patient Disposition

An overview of patient populations will be summarized by treatment group. Frequency counts and percentages of patients excluded prior to first dose by primary reason for exclusion will be provided for patients who failed to meet study entry requirements during screening.

Patient disposition will be summarized using the mITT population. Frequency counts and percentages of patients who complete the study treatment visits or discontinue early from Study JAHW, along with whether they completed follow-up or did not complete follow-up, will be summarized separately by treatment group for patients along with their reason for study discontinuation. Frequency counts and percentages of patients who complete the treatment or discontinue treatment early will also be summarized separately by treatment group for patients, along with their reason for treatment discontinuation.

A listing of patient disposition will be provided for all randomized patients, with the extent of their participation in Study JAHW and the reason for discontinuation. A listing of all randomized patients with their treatment assignment will also be provided.

6.7. Patient Characteristics

Patient characteristics, including demographics and baseline characteristics, will be summarized descriptively by treatment group for the mITT population. Historical illnesses and pre-existing conditions will be summarized descriptively by treatment group for the safety population.

Descriptive statistics including number of patients (n), mean, SD, minimum, 1st quartile, median,

3rd quartile, and maximum will be provided for continuous measures, and frequency counts and percentages will be tabulated for categorical measures. A listing of patient demographics will also be provided for the mITT population. No formal statistical comparisons will be made among treatment groups unless otherwise stated.

Table JAHW.6.2 describes the specific variables and how they will be summarized.

Table JAHW.6.2. Patient Characteristics

Variable	Continuous Measure Summary	Categorical Summary
Age ^a	Yes	12 to <18 years, 9 to <12 years, 6 to <9 years and 2 to <6 years
Sex	No	Male, Female
Race	No	American Indian/Alaska Native, Asian, Black/African American, Native Hawaiian or other Pacific Islander, White, or Multiple
Geographic region	No	By Country
Height (cm)	Yes	None
Weight (kg)	Yes	<20kg, 20 to < 30 kg, ≥30kg
BMI ^b	Yes	Underweight (<18.5 kg/m ²), Normal (≥18.5 and <25 kg/m ²), Overweight (≥25 and <30 kg/m ²), Obese (≥30 and <40 kg/m ²), Extremely obese (≥40 kg/m ²)
Alcohol use	No	Never, Current, Former
Tobacco use	No	Never, Current, Former
Prior JIA-U therapy	No	Never used, Ever used
Prior MTX use	No	Never used, Ever used
Prior bDMARD-IR use	No	Never used, Ever used
Duration of uveitis diagnosis (years) ^a	Yes	0 to <2 years, 2 to <5 years, 5 to <10 years, ≥10 years
Age at uveitis onset (years) ^a	Yes	12 to <18 years, 9 to <12 years, 6 to <9 years and 0 to <6 years
Type of uveitis	No	Active JIA-U, chronic anterior ANA-positive uveitis
Baseline number of active joints	Yes	None
Baseline number of joints with limited range of motion	Yes	None
Baseline Physician's Global Assessment of Disease Activity	Yes	None
Baseline Parent's Global Assessment of Well-Being	Yes	None
Baseline CHAQ Physical Function	Yes	None
Baseline ESR	Yes	
Baseline Juvenile Arthritis Disease Activity Score (JADAS)-27	Yes	None

Abbreviations: ANA = Anterior Antinuclear Antibody; bDMARD = biological disease-modifying antirheumatic drug; BMI = body mass index; CHAQ = Childhood Health Assessment Questionnaire;; ESR = erythrocyte sedimentation rate; JADAS-27 = Juvenile Arthritis Disease Activity Score-27; JIA-U = juvenile idiopathic arthritis-associated uveitis; MTX = methotrexate.

- a In case the date of birth is missing, age in years will be calculated as length of the time interval from the imputed date of birth (15th of birth month collected in the electronic case report form to the informed consent date).
- b BMI will be calculated as: $BMI (kg / m^2) = Weight (kg) / (Height [m])^2$.

6.8. Treatment Compliance

Treatment compliance with investigational product will be summarized for each treatment period with corresponding population. Patients will be considered compliant for each treatment period if they miss <20% of the expected doses (unless the patient's investigational product was withheld by the investigator for safety reasons). The proportions of patients compliant will be summarized.

Similarly, patients will be considered noncompliant if they are judged by the investigator to have intentionally or repeatedly taken more than the prescribed amount of study medication.

Compliance for baricitinib:

Compliance to baricitinib in the period of interest will be calculated as follows:

$$\text{Compliance} = \frac{\text{total number of tablets (or weight of suspension) dispensed} - \text{total number of tablets (or weight of suspension) returned}}{\text{expected number of total tablets (or weight of suspension)}}$$

where

Total number of tablets (or weight of suspension) dispensed: sum of tablets (or weight of suspension) dispensed in the period of interest prior to Visit x ;

Total number of tablets (or weight of suspension) returned: sum of the tablets (or weight of suspension) returned in the period of interest prior to and including Visit x ;

Expected number of tablets (or weight of suspension): number of days in the period of interest \times number of tablets (or weight of suspension) taken per day = $[(\text{date of visit} - \text{date of first dose} + 1) - \text{number of days of temporary drug interruption}] \times \text{number of tablets (or weight of suspension) taken per day}$

If a patient has dose interrupted for safety reasons during the period, the total number of days drug was withheld will be deducted from the expected total # of tablets (or weight of suspension) used.

Compliance for injections (adalimumab):

Compliance to adalimumab the period of interest will be calculated as follows:

$$\frac{\text{actual total # of syringes used}}{\text{Expected total # of syringes used}} \times 100$$

Where:

Expected total number of syringes used = integer of [(total number of days in the period of interest)/14] + 1.

Actual total # of syringes used = total # of syringes dispensed – total # of syringes returned.

For patients with drug interruptions, the expected number of syringes used will be calculated for the period before and after interruption in the period of interest separately, then the sum of the two will be the expected total for the period of interest.

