5.1.4. Post-Treatment Follow-Up Period

Patients who complete the study or discontinue early from the study will return for the post-treatment safety follow-up visit (Visit 801) approximately 28 days after the last dose of investigational product.

Patients who have received at least 1 dose of investigational product and terminate participation early must have an early termination visit (ETV).

Patients who have discontinued investigational product but remain in the study for more than 28 days without investigational product will have an ETV if they choose to withdraw from the study; however, a separate follow-up visit (Visit 801) is not required.

Patients should not initiate new treatment during the post-treatment follow-up period. However, if patients or investigators must initiate a new treatment, patients should complete a Visit 801 prior to the first dose of the new therapy (if possible).

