7.6. Treatment Compliance

Patient compliance with study medication will be assessed during the treatment period of Part A and Part B per the Schedule of Activities.

Patients treated with baricitinib or adalimumab will be considered noncompliant if they miss $\geq 20\%$ of the prescribed doses during the study (unless the patient's investigational product was withheld by the investigator for safety reasons). For adalimumab, a patient will be considered significantly noncompliant if his or her study medication compliance rate is $< 80\%$ or if there are any consecutive missed injections, unless the patient's investigational product was withheld by the investigator for safety reasons.

Similarly, patients will be considered noncompliant if they are judged by the investigator to have intentionally or repeatedly taken more than the prescribed amount of study medication. Patients found to be noncompliant with the investigational product should be assessed to determine the reason for noncompliance and educated and/or managed as deemed appropriate by the investigator to improve compliance.

Patients will be counseled by study staff on the importance of taking the investigational product as prescribed, as appropriate.

Patient compliance will be further defined in the statistical analysis plan (SAP).

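### SAP 6.8 keeps counting expected baricitinib doses after a permanent stop, so a fully adherent child who stops for a non-safety reason but stays in the study is scored as noncompliant

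*SAP*

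**What the plan says.** Protocol 7.6 and 10.3.2.4 leave the detailed definition of compliance to the SAP. SAP 6.8 gives it for baricitinib as a ratio.

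- **Numerator:** tablets (or weight of suspension) "dispensed in the period of interest prior to Visit" x, minus what was returned up to and including that visit.
- **Denominator:** days from first dose to the visit date, plus one, less the "number of days of temporary drug interruption", times the daily number of tablets.
- **Threshold:** "Patients will be considered compliant for each treatment period if they miss <20% of the expected doses".

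SAP 6.8 also has two safety provisions. The threshold carries an exception where "investigational product was withheld by the investigator for safety reasons", as does Protocol 7.6 ("unless the patient's investigational product was withheld by the investigator for safety reasons"). The second provision reduces the denominator: "If a patient has dose interrupted for safety reasons during the period, the total number of days drug was withheld will be deducted".

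For adalimumab, expected syringes are the whole number of 14-day intervals in the period of interest, plus one. SAP 6.8 does not define the period of interest, or Visit x, for a child who stops early.

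The protocol treats temporary interruption (8.1.1) and permanent discontinuation (8.1.2) as different events. Section 5.1.4 refers to "Patients who have discontinued investigational product but remain in the study for more than 28 days without investigational product". SAP 6.6 tabulates the two kinds of stopping separately. Alongside study discontinuation, "Frequency counts and percentages of patients who complete the treatment or discontinue treatment early will also be summarized separately by treatment group".

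**The concern.** The denominator should count doses the child was meant to take. Once study drug is stopped for good, none is due. The SAP formula nevertheless runs to the visit date, and its only subtraction covers temporary holds. Each day between a permanent stop and the visit is then scored as a missed dose.

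The SAP handles this event elsewhere. Section 6.3.2 carries forward the last observation on or before permanent treatment discontinuation, and 6.6 reports treatment discontinuation with its reason. Only 6.8 omits it.

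At stake is the meaning of the compliance table. Children who took every dose and then stopped, for example at the family's request or for lack of efficacy, would appear beside children who skipped doses. In a small trial that could suggest poor adherence lay behind nonresponse when it did not. It also lets two programmers report very different values for the same child, depending on where each ends the count.

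**Working it through.** The documents state no compliance figure, so there is nothing of theirs to reproduce.

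**Inputs**
- Ratio and deduction: SAP 6.8.
- Visit days: Week 8 = Day 56, Week 12 = Day 84, Week 16 = Day 112, Week 20 = Day 140, Week 24 = Day 168, with a window of ±4 days (Protocol Section 2).
- Assumptions: first dose on Day 0; one tablet a day; all unused tablets returned; perfect adherence until a permanent stop at Week 8 (56 tablets, or 57 if the Week 8 dose is taken); no temporary interruption; no safety deduction.

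**Formula**

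Compliance = tablets taken / [(visit day − 0 + 1) − interruption days]

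**Check on a completer.** At Week 24 the denominator is 168 + 1 = 169. A fully adherent child scores 168/169 = 99.4% or 169/169 = 100%, so the formula works for completers.

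**Child who stops at Week 8**

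| Visit used | Denominator | 56 taken | 57 taken |
|---|---|---|---|
| Early termination visit, Day 56 | 57 | 98.2% | 100% |
| Week 12 | 85 | 65.9% | 67.1% |
| Week 16 | 113 | 49.6% | 50.4% |
| Week 20 | 141 | 39.7% | 40.4% |
| Week 24 | 169 | 33.1% | 33.7% |

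Across the Week 24 window the range is 56/173 = 32.4% to 57/165 = 34.5%.

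**When the child fails the rule.** Compliance requires a ratio above 80%.
- With 56 tablets (last dose Day 55), a visit 14 days later gives 56/70 = 80.0%. Exactly 20% is missed, so the rule is not met.
- With 57 tablets (last dose Day 56), 14 days later gives 57/71 = 80.3% and 15 days later gives 57/72 = 79.2%.

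The crossing is therefore about two weeks after the last dose.

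**Later stops, assessed at Week 24**
- 112 tablets: 112/169 = 66.3%.
- 135 tablets: 135/169 = 79.9%, not compliant.
- 136 tablets: 136/169 = 80.5%, compliant.

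**Adalimumab, only if the period of interest runs through Week 24.** Expected syringes = integer(168/14) + 1 = 13. A child injected on Days 0, 14, 28, 42 and 56 who then stops has used 5, giving 5/13 = 38%. If the period ends on Day 56, expected = integer(56/14) + 1 = 5, giving 5/5 = 100%. The SAP does not say which applies.

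**After the fix.** Ending the baricitinib count at the last dose gives 56/56 or 57/57 = 100%.

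**Weight in the table.** One child is 1/20 = 5 points in a baricitinib arm of 20. In an adalimumab arm of 4 one child would be 1/4 = 25 points, under the conditional reading above. The documents give no expected number of such children.

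**The case against.** The best defence is that 6.8 is under-defined rather than wrong. The expected count is first described as days in the period of interest, a term left open, and Protocol 7.6 speaks of prescribed doses, of which there are none after a permanent stop. That would support a sensible reading, but 6.8 goes on to write the count out explicitly with the visit date as its end. A programmer following that line gets 33%.

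Several stronger readings are tempting, and the documents do not support them.

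- **That any early stop scores 33%.** This needs continued visits to Week 24. A child who leaves has an early termination visit at which compliance is assessed, and scores about 98% to 100% if it falls at the stop. Protocol 8.2 also requires a child who needs an excluded therapy to leave the study before it starts, which removes some stoppers from the affected group.
- **That a child who stops for an adverse event is necessarily tabulated as noncompliant.** SAP 6.8 has two safety provisions. If they cover permanent discontinuation, the off-drug days are deducted and the result is 100%. If they cover temporary holds only, it can be 33%. The wording about interruption leans towards temporary holds, but the SAP does not settle it.
- **That the SAP contradicts the protocol's safety exemption.** It carries the same exemption, so no contradiction is shown.
- **That the adalimumab formula has the same error.** It contains no visit date. The problem there depends on an undefined end to the period.
- **That efficacy conclusions are affected.** Compliance defines neither the mITT nor the safety population (SAP 6.1.1) and does not enter the primary analysis (SAP 7.1). Discontinuation with its reason (6.6) and exposure (8.1) are reported separately, so a careful reader can tell stopping from skipping.

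What remains is the non-safety stop in a child who stays in the study. No exemption covers that case.

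**Conclusion.** Wrong as written, minor, and confined to a descriptive table. For a fully adherent child who permanently stops baricitinib for a non-safety reason and remains in the study, SAP 6.8 scores every later day up to the visit as a missed dose. After a Week 8 stop the score is 33% at Week 24, and the child fails the compliance rule from about two weeks after the last dose.

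This rests on one tablet a day, full return of unused drug, and Visit x being a visit after the stop. For safety stops and for adalimumab the outcome is undetermined until the SAP defines its terms. How many children would be affected cannot be estimated from the documents.

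**What to change.** In SAP 6.8:

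1. End the expected baricitinib count at the earlier of the visit date and the date of last dose at permanent discontinuation of investigational product.
2. End the adalimumab period of interest at the same date.
3. State that days after permanent discontinuation are not counted as missed doses, whatever the reason for stopping. This also settles whether safety stops are covered.

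Leave the planned disposition tables (SAP 6.6) and the tables of discontinuation due to adverse events (SAP 8.2) as they are. The latter serve a secondary safety endpoint and should not be folded into disposition.

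The cost is a short SAP edit and a small programming change. No new data are needed: the last-dose date is already required for the post-baseline periods in SAP Table JAHW.8.1 and for exposure in 8.1.

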that the baricitinib treatment response is greater than 57%, otherwise the study will be considered negative.

Efficacy and health outcome endpoints will be summarized using descriptive statistics. The last-observation-carried-forward approach will be used to impute missing data.

Categorical data will be summarized as frequency counts and percentages. The proportions and 95% confidence interval will be reported. Missing data will be imputed using the modified nonresponder imputation method.

Two interim analyses will be performed to determine if the study should be stopped for futility when 10 and 20 baricitinib-treated patients have completed 24 weeks of treatment. At each interim analysis, the posterior probability of the treatment response rate being lower than 40% will be calculated, and the study will be stopped if this probability is greater than 75% (otherwise the study will continue).

Descriptive response rates will be evaluated in adalimumab-treated patients.

An analysis will evaluate response rates in MTX-IR adalimumab-treated patients and MTX-IR baricitinib-treated patients.

All safety data will be descriptively summarized using corresponding populations.

Ethical Considerations of Benefit/Risk

Based on the efficacy of baricitinib demonstrated in the Phase 3 RA program and the observed safety profile, the probability of a positive benefit/risk warrants this study to be conducted, given the unmet need in patients with JIA-U and ANA-positive uveitis.

2. Schedule of Activities

The Schedule of Activities described below should be followed for all participants enrolled in Study JAHW. In the event participation in this study is affected by exceptional circumstances (such as pandemics or natural disasters), please refer to Appendix 9 and consult with the sponsor's representative for additional guidance.

Table JAHW.1. Schedule of Activities

Visit #	Screening		Treatment Period Part A							Early Termination	Post-Treatment Follow-Up						
	V1	V1a	V2 ^a Baseline	V3	V4	V5	V6	V7	V8								
Study Week			W0	W4	W8	W12	W16	W20	W2 4	Any Week							
Study Day (Approximately)	-42 to -1		0	28	56	84	112	140	168	Any Day							28 ± 5 Days after Last Dose
Visit Window (Days)				±4													
Informed consent and assent ^d	X																
Complete medical history	X																
Immunization record	X		X	X	X	X	X	X	X								
Demographics	X																
Physical examination ^e	X																
Tanner Stage Scale ^z			X														

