7.2.1. Selection and Timing of Doses

Baricitinib:

Baricitinib should be administered at approximately the same time each day. Patients will receive the final age-based dose of baricitinib selected in the PK assessment period of Study JAHV. Based on PBPK modeling, this is expected to be 4-mg for patients ≥ 9 to < 18 years of age and 2-mg for patients < 9 years of age, in order to produce exposures similar to those in adults after 4-mg QD administration; see [Appendix 8](#) for updated dosing based on the current data. Refer to Section [5.5](#) for additional information.

Adalimumab:

Adalimumab will be administered as a subcutaneous injection once every 2 weeks. The dose will be based on body weight: 20 mg every 2 weeks for participants weighing < 30 kg, or 40 mg every 2 weeks for patients weighing ≥ 30 kg (adalimumab SmPC).

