4.2. Secondary Objectives

The secondary objectives of Study JAHW are grouped according to 2 periods defined in the study design:

Treatment Period Part A: 24 weeks

Treatment Period Part B: 260 weeks.

Baricitinib patients who complete Part A may continue to Part B, the open-label extension (OLE) period of Study JAHW. Patients on adalimumab will be discontinued after Week 24. Patients who do not continue in the OLE will have a follow-up visit (Visit 801) approximately 28 days after the last dose of the investigational product.

In particular, for Study JAHW, the secondary estimand is defined by

Population of interest: the population of interest for Part A of Study JAHW is patients who participate in Study JAHW Part A. The population of interest for Part B is patients who stay in Study JAHW Part B. Study JAHW patients are patients from 2 years to <18 years old with active JIA-U or chronic anterior ANA-positive uveitis. Analysis populations are defined in Section 6.1.1.

Variable (or endpoint) of evaluation: primary and secondary endpoints/variables are listed in [Table JAHW.4.1](#) and [Table JAHW.4.2](#). A full list of endpoints and variables is given in [Table JAHW.7.1](#) and [Table JAHW.7.2](#).

Population-level summary: the summary measure for binary variables will be proportion and the summary measure for continuous variables will be the average.

Intercurrent event(s) strategy: in Study JAHW Part A, for efficacy and health outcomes-related endpoints, the analysis population will be based on patients who have had the chance to complete the visits. In the estimand framework, for binary variables other than the primary outcome variable, the composite estimand strategy will be applied; nonresponder imputation will be applied to variables to support this strategy. The while-on-treatment strategy will be used for continuous variables, and last observation carried forward (LOCF) imputation will be used to support this strategy. For Part B, the analysis population will be based on completers for the specific analysis visit, and this method is referred as the as-observed analysis. The details of the imputation methods for the estimand and intercurrent events are described in Section 6.3. Statistical methods corresponding to each of the efficacy and health outcomes variables are summarized in [Table JAHW.7.1](#), [Table JAHW.7.3](#), [Table JAHW.7.3](#), and [Table JAHW.7.4](#).

The secondary objectives of Study JAHW are described in [Table JAHW.4.2](#).

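### The adalimumab compliance formula in SAP 6.8 expects 13 syringes in Part A against 12 scheduled doses if no Week 24 dose is counted, which can reclassify a patient who missed two

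*SAP*

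**What the plan says.** SAP 6.8 defines adalimumab compliance as syringes used over syringes expected. The denominator is "Expected total number of syringes used = integer of [(total number of days in the period of interest)/14] + 1". The numerator is "total # of syringes dispensed" minus those returned. After a drug interruption, "the expected number of syringes used will be calculated for the period before and after interruption in the period of interest separately", and the two counts are added. A patient is compliant for a treatment period if fewer than 20% of expected doses are missed.

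For baricitinib the same section gives two rules that it does not give for adalimumab. It counts only drug "dispensed in the period of interest prior to Visit" x, and it defines days as visit date minus first-dose date plus 1.

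Protocol 7.2.1 sets the interval: "Adalimumab will be administered as a subcutaneous injection once every 2 weeks". SAP 4.2 gives "Treatment Period Part A: 24 weeks" and, like Protocol 5.1.3, discontinues adalimumab patients after Week 24. For adalimumab, Protocol 7.6 adds that "a patient will be considered significantly noncompliant if his or her study medication compliance rate is" below 80%, or if consecutive injections are missed.

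**The concern.** The nominal Part A visits (Days 28, 56, 84, 112, 140 and 168) are all exact multiples of 14 days. On such a day, the integer part plus 1 includes the dose due on the visit day itself. If that dose is not in the numerator, the denominator is one too high. At interim visits this might come right later, but at Week 24 it cannot if treatment ends with the Week 22 dose. With a cut-off at 80% and a denominator of only 12 or 13, one syringe can decide the class. In an arm of four patients, one changed class moves the reported proportion compliant by 1/4 = 25 percentage points.

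**Working it through.** **Inputs.** Interval 14 days (Protocol 7.2.1). Part A 168 days (SAP 4.2). Nominal visit days and a window of ±4 days (Protocol Section 2, Table JAHW.1). Cut-off: under 20% missed, per treatment period (SAP 6.8). The SAP gives no worked compliance figure, so there is none to reproduce. Assumption: the dose due on the visit day is not counted.

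**Formulas.** D = visit date minus first-dose date. SAP expected = int(D/14) + 1. Due before the visit (Days 0, 14, 28 and so on, before D) = ceiling(D/14).

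**1. Nominal visit days, full adherence**

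| Visit | D | SAP expected | Due before visit | Score |
|---|---|---|---|---|
| Week 4 | 28 | 3 | 2 | 66.7% |
| Week 8 | 56 | 5 | 4 | 80.0% |
| Week 12 | 84 | 7 | 6 | 85.7% |
| Week 16 | 112 | 9 | 8 | 88.9% |
| Week 20 | 140 | 11 | 10 | 90.9% |
| Week 24 | 168 | 13 | 12 | 92.3% |

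**2. Part A classification, Week 24 visit on Day 168**

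| Missed of 12 | Out of 12 | Out of 13 (SAP) | Class |
|---|---|---|---|
| 0 | 100% | 92.3% | compliant either way |
| 1 | 91.7% | 84.6% | compliant either way |
| 2 | 83.3% | 76.9% | compliant, becomes noncompliant |
| 3 | 75.0% | 69.2% | noncompliant either way |

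**3. Visit window.** For a patient who used 10 syringes:
- Day 166: int(166/14) + 1 = 12, so 10/12 = 83.3%, compliant.
- Day 168: 13, so 10/13 = 76.9%, noncompliant.
- Day 167: 12 if days are D. If days are D + 1, as for baricitinib, int(168/14) + 1 = 13.
- Days 169 to 172: 13. This is right only if a Day 168 dose was due; it is one too many if treatment ended with the Week 22 dose.

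At Week 4, SAP expected and due agree on Days 24 to 26 (2 and 2) and Days 29 to 32 (3 and 3). They differ on Day 28, and also on Day 27 if days are D + 1.

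**4. Early termination.** If the period ends exactly on Day 28, full adherence scores 2/3 = 66.7%. On Day 56 it scores 4/5 = 80.0%, which is exactly 20% missed and so fails the under-20% rule.

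**5. Interruptions**, with dosing restarted on the day of resumption:
- Hold Day 20, restart Day 34 (segments 20 and 134 days): SAP (1+1) + (9+1) = 12; due 2 + 10 = 12. Excess 0.
- Hold Day 50, restart Day 70 (50 and 98 days): SAP (3+1) + (7+1) = 12; due 4 + 7 = 11. Excess 1.
- Hold Day 70, restart Day 84 (70 and 84 days): SAP (5+1) + (6+1) = 13; due 5 + 6 = 11. Excess 2. Full adherence scores 11/13 = 84.6%; one missed dose scores 10/13 = 76.9% instead of 10/11 = 90.9%.

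Over 6,709 combinations (hold starting Day 1 to 149, lasting 7 to 56 days, restart before Day 168, visit on Day 168, days counted as D), the excess is 0 in 5,826, 1 in 849 and 2 in 34. It arises only from a segment that is an exact multiple of 14 days. If doses instead stay on the original calendar, the excess is 1 in 6,254 and 2 in 455, so an interruption usually adds nothing to the one already present at Day 168.

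**The case against.** The +1 is not wrong in itself. It correctly counts the doses from Day 0 through the visit day inclusive, and if the visit-day dose also enters the numerator, full adherence scores 100% at every nominal visit. The SAP does not exclude that dose for adalimumab; the rule limiting the numerator to drug dispensed before the visit is written for baricitinib only. This stands, and it makes the finding conditional. It does not remove it: the SAP does not include the dose either, and patients stop adalimumab after Week 24.

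A reader might infer three stronger things from the table.
- **Adherent patients are misclassified from Week 4 on.** Protocol 10.3.2.4 has compliance assessed at each visit, but both documents classify by period. A fully adherent, uninterrupted completer scores 92.3% and passes.
- **The count is one too high at every scheduled visit.** At interim visits the excess disappears on most days of the ±4-day window.
- **Every interruption adds a further syringe.** With dosing restarted on resumption, the second +1 usually counts the restart dose correctly.

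Protocol 7.6 also already treats consecutive missed injections as significant noncompliance, so under that rule the reclassification in step 2 matters only when the two misses are apart. SAP 6.8 does not carry that rule over.

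**Conclusion.** The formula gives a wrong denominator in a definable case: a 168-day Part A with no adalimumab dose counted at Week 24, where it expects 13 syringes against 12. The patients affected are those near the cut-off (2 of 12 missed: 76.9% instead of 83.3%), those whose period ends exactly on Day 28 or Day 56, and those with an interruption segment of an exact multiple of 14 days. The early-termination case also assumes that the period ends at that visit, which the SAP does not define. That the class can turn on the visit day within the permitted window is a weakness under either day count.

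The importance is low. Compliance is summarised descriptively and defines no analysis population in SAP 6.1.1. No treatment comparison is planned, and the adalimumab arm needs at least 4 evaluable patients. A reader might infer that the efficacy results are affected; nothing in the documents supports that.

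**What to change.** In SAP 6.8, replace the expected count with the number of scheduled two-weekly doses due from first dose up to, but not including, the visit day or the day treatment stops: ceiling(D/14), with D = visit date minus first-dose date (no +1), and a maximum of 12 for Part A. Apply it to each on-treatment segment, with D for the earlier segment ending at the start of the hold, and state how the restart dose is counted. In the numerator, count only syringes dispensed before that visit, as is already done for baricitinib.

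Check: Week 4 gives 28/14 = 2, Week 24 gives 168/14 = 12, and the 70 + 84 day case gives 5 + 6 = 11, so full adherence scores 100% in each.

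Changing only the integer term to (days − 1)/14 is not enough. If days are counted inclusively, as for baricitinib, Day 28 is 29 days and int(28/14) + 1 is still 3. If the sponsor does intend a Week 24 dose to count, the SAP should say so and include that syringe in the numerator; 13 would then be right.

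The cost is one formula and two or three sentences in the SAP, with no protocol change.
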